6.7 Overdose

There is limited clinical experience with ATI-450. In the event of an overdose, patients should receive appropriate supportive medical care and be followed until resolution/stabilization of any clinical issues.

Any instance of overdose (suspected or confirmed and irrespective of whether or not it involved ATI-450) must be communicated to the sponsor (or a specified designee) within 24 hours of its occurrence.

Any overdose associated with clinical symptoms will be recorded as an AE or SAE, as appropriate. Details of any signs or symptoms and their management should be recorded, including details of any treatments administered for the overdose. All overdoses with clinical symptoms meeting the SAE criteria must be reported as described in Section 7.4.

6.8 Compliance

The investigator (or designee) will explain the correct use of the study medication to each patient and will check that each patient is following the instructions properly. Compliance will be assessed at each visit by counting returned tablets and will be documented in the source documents and eCRF. Any deviation from the correct use of the study medications will be recorded in the eCRF.

A record of the number of tablets dispensed to and taken by each patient will be maintained and reconciled with study medication and compliance records. The study medication start and stop dates, including dates for study medication delays and/or dose reductions, will also be recorded in the eCRF.

6.9 Accountability

The study medication must not be used for any purpose other than that defined in this protocol. All supplies of study drug will be accounted for in accordance with Good Clinical Practice (GCP).

The site pharmacist or (designee) should maintain accurate records of all study medication supplies received during the study. These records should include the dates and amounts of study medication that were received at the site, dispensed, and destroyed or returned to the sponsor (or designee). The records should include dates, quantities, batch/serial numbers, expiration dates (if applicable), and the unique code numbers assigned to the study medication and study patients. If errors or damage in the study medication shipments occur, the investigator should contact the sponsor (or its designee) immediately. Copies of the study medication accountability records will be provided by each investigator for inclusion in the trial master file (TMF). The study monitor will periodically check the supplies of study medication held by the investigator or pharmacist to verify accountability of the study medication used.

Page 46 of 71

The investigator (or designee) will administer the study medication only to the identified patients in this study, according to the procedures described in this study protocol.

After the end of the study, all unused study medication and all medication containers should be destroyed at the study center or returned to the sponsor (or designee) for destruction. In either instance, complete documentation will be returned to the sponsor.

7 ADVERSE EVENTS

7.1 Definitions

7.1.1 Adverse Events

An AE is any untoward medical occurrence in a patient or clinical study patient administered a pharmaceutical product and which does not necessarily have a causal relationship with this treatment. An AE can therefore be any unfavorable and unintended sign (including an abnormal laboratory finding), symptom, or disease temporally associated with the use of a medicinal (investigational) product, whether or not related to the medicinal (investigational) product.

7.1.2 Serious Adverse Events

An SAE is any untoward medical occurrence that meets any of the following criteria:

- Results in death.
- Is life-threatening.
- Requires inpatient hospitalization or prolongation of existing hospitalization.
- Results in persistent or significant disability/incapacity.
- Is a congenital anomaly/birth defect.
- Is an important medical event that may not result in death, be life-threatening, or require hospitalization. The event will be considered an SAE when, based upon appropriate medical and scientific judgment, the event may jeopardize the patient and may require medical or surgical intervention to prevent one of the outcomes listed above. Examples of such events include: intensive treatment in an emergency room or at home for allergic bronchospasm, blood dyscrasias or convulsions that do not result in inpatient hospitalization, or the development of drug dependency or drug abuse.

Definition of Terms

Life-threatening: an AE is life-threatening if the patient was at immediate risk of death from the event as it occurred; i.e., it does not include a reaction that, if it had occurred in a more severe form, might have caused death. For example, drug-induced hepatitis that resolved without evidence of hepatic failure would not be considered life-threatening even though drug-induced hepatitis can be fatal. It does not include an AE or suspected adverse reaction that, had it occurred in a more severe form, might have caused death.

Hospitalization: AEs requiring hospitalization or prolongation of hospitalization should be considered SAEs. Hospitalization for elective surgery, or for procedures planned prior to the patient providing informed consent, or routine clinical procedures that are not the result of an AE

(e.g., elective surgery for a pre-existing condition that has not worsened) need not be considered AEs or SAEs. If anything untoward is reported during the procedure, that occurrence must be reported as an AE or SAE as per the definitions.

In general, hospitalization signifies that the patient has been detained (usually involving at least an overnight stay) at the hospital or emergency ward for observation and/or treatment that would not have been appropriate in the physician's office or outpatient setting. When in doubt as to whether hospitalization occurred or was necessary, the AE should be considered serious.

Disability/incapacity: an AE is incapacitating or disabling if the experience results in a substantial and/or permanent disruption of the patient's ability to carry out normal life functions.

7.1.3 Clinical Laboratory Abnormalities and Other Abnormal Assessments

Laboratory abnormalities without clinical significance should not be recorded as AEs or SAEs. However, laboratory abnormalities (e.g., clinical chemistry, hematology, coagulation, lipids, and urinalysis abnormalities) that require medical or surgical intervention or lead to study medication interruption, modification, or discontinuation must be recorded as an AE or SAE, as applicable. In addition, laboratory or other abnormal assessments (e.g., in ECGs, X-rays, or vital signs) that are associated with signs and/or symptoms must be recorded as an AE or SAE if they meet the definition of an AE or SAE as described in Sections 7.1.1 and 7.1.2. If the underlying cause for the laboratory abnormality is known, record the etiology or diagnosis (e.g., anemia), rather than the laboratory result (i.e., decreased hemoglobin).

For specific information on handling of clinical laboratory abnormalities, see Section 5.3.2.

7.2 Assessment of Adverse Events

7.2.1 Severity

The investigator will determine the intensity of the AE according to the definitions below:

- **Mild:** An event that is easily tolerated by the participant, causing minimal discomfort, and not interfering with everyday activities
- **Moderate**: An event that causes sufficient discomfort and interferes with normal everyday activities
- Severe: An event that prevents normal everyday activities. An AE that is assessed as severe should not be confused with a SAE. Severe is a category utilized for rating the intensity of the event; both AEs and SAEs can be assessed as severe. An event is defined as "serious" when it meets at least 1 of the pre-defined outcomes as described in the definition of an SAE, not when it is rated as severe.

7.2.2 Causality

The investigator is obligated to assess the relationship between study medication and each occurrence of an AE/SAE. The investigator will use her/his best clinical judgment to determine the relationship. Alternative causes, such as underlying disease(s), concomitant therapy, and other risk factors, as well as the temporal relationship of the event to study intervention administration, will be considered and investigated. The investigator will also consult the IB in his/her assessment. The investigator will define the relationship of an AE to the study medication by selecting one of the following categories:

Related:

• There is a reasonable possibility that there is a causal relationship between the study medication and the AE

Not Related:

• There is no reasonable possibility that there is a causal relationship between the study medication and the AE

A "reasonable possibility" of a relationship conveys that there are facts, evidence, and/or arguments to suggest a causal relationship, rather than a relationship cannot be ruled out.

7.3 Documenting and Reporting Adverse Events

Reporting of SAEs will begin when the patient has provided informed consent and will continue up to the end of study visit or 30 days after the last ATI-450administration whichever is later. Reporting of AEs will begin when the patient receives the first dose of ATI-450 and will continue up to the end of study visit or 30 days after the last study drug administration, whichever is later. Any clinical AE that occurs between the time of consent and dosing Day 1 will be recorded as medical history.

Occurrence of AEs may be volunteered spontaneously by the patient; discovered as a result of general, nonleading verbal questioning by the study staff; or determined by physical examination or other safety assessments. All AEs will be monitored and recorded in the CRF throughout the entire study.

For all AEs, the investigator must pursue and obtain adequate information (a description of the event, severity, time of occurrence [including whether the AE onset was before, during, or after the study medication administration if the AE started on a dosing day], duration, and any action [e.g., treatment/follow-up tests]). The outcome of the event should be provided along with the investigator's assessment of the relationship to the study medication. The investigator must also assess whether the event meets the criteria for classification as an SAE.

It is the investigator's responsibility to review all documentation (e.g., hospital notes, laboratory reports, and diagnostic reports) related to an AE. Wherever possible, the investigator's diagnosis, not the individual signs and symptoms, will be documented as the AE.

Investigators are not obligated to actively seek AEs or SAEs after the patient's conclusion of study participation. However, if the investigator learns of any SAE, including death, at any time after a patient has been discharged from the study, and he/she considers the event to be reasonably related to the study medication or study participation, the investigator must promptly notify the sponsor.

7.4 Reporting of Serious Adverse Events

Upon becoming aware of a SAE whether or not related to the study medications, the investigator must:

- 1. Take the appropriate medical action to ensure the patient's safety.
- 2. Immediately, and no longer than within 24-hours, report the SAE to the safety monitor, ensuring that the patient information is de-identified to (Aclaris safety monitor):

ProPharma Group

- Email:
- Fax:
- 3. Print a copy of the email confirmation from ProPharma and place in the study file.
- 4. Within 24-hours, complete, as fully as possible an SAE form; email the forms and any other relevant information (e.g., concomitant medication eCRF, medical history eCRF, laboratory test results) to ProPharma.
- 5. Monitor and document the progress of the SAE until it resolves or, if not resolved after the patient's last study visit, until in the opinion of the investigator the AE reaches a clinically stable outcome with or without sequelae AND the investigator and Aclaris safety and medical monitor agree that the SAE is satisfactorily resolved.
- 6. Report any SAE updates within 24-hours of knowledge to the safety monitor via email (or fax) and update the SAE form.
- 7. Comply with the appropriate regulatory requirements and Aclaris instructions regarding reporting of the SAE to the responsible IRB.

The investigator is obliged to respond to any request for follow-up information (e.g., additional information, event outcome, final evaluation, or other records where needed) or to any question the sponsor (or designee) may have concerning the SAE within the same timelines as those noted above for initial reports. This is necessary to ensure prompt assessment of the event by the

sponsor (or designee) and, as applicable, to allow the sponsor to meet strict regulatory timelines associated with expedited reporting obligations for events of this nature.

7.5 Adverse Event and Serious Adverse Event Follow-up

During the study (and after the end of study visit), all AEs and SAEs should be followed proactively by the investigator until the event resolves or the condition stabilizes to a level acceptable to the investigator, until the event is otherwise explained, or until the patient is lost to follow-up. At the time the patient's study participation ends, all ongoing AEs and SAEs should be evaluated for resolution. New or updated information will be recorded in the originally completed eCRF and the investigator will submit any updated SAE information to the sponsor within 24 hours of receipt of the information.

7.6 Safety Reporting Oversight

In accordance with ICH GCP, the sponsor (or designee) will inform investigators of "findings that could affect adversely the safety of patients, impact the conduct of the trial, or alter the IRB/IEC approval/favorable opinion to continue the trial."

The sponsor has a legal responsibility to notify both the local regulatory authority and other regulatory agencies about the safety of a study medication under clinical investigation. The sponsor will comply with country-specific regulatory requirements relating to safety reporting to the regulatory authority, IRB/IEC, and investigators. To support compliance with these requirements, the investigator must provide requested information in a timely manner.

An investigator who receives an investigator safety report describing SAEs or other specific safety information (e.g., summary or listing of SAEs) from the sponsor will file it along with the IB and will notify the IRB/IEC, if appropriate, according to local requirements.

8 STATISTICS

8.1 General Procedures

Analyses will be performed using SAS® (SAS Institute, Cary, NC, US) by the sponsor or its representatives.

The statistical analysis plan (SAP) will be approved prior to any lock of the study database and unblinding of the study data. The SAP will provide a detailed description of the statistical methods and expand on the details provided in the protocol.

Descriptive statistics (number of observations, mean, standard deviation, median, minimum, and maximum) will be provided for continuous variables, and counts and percentages will be presented for categorical variables.

Baseline is defined as the last non-missing measurement before or on the date of first administration of study medication.

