In the event of an SAE, the investigator will send a safety report form within 24 hours of becoming aware of the SAE to:

ProPharma Group		
FAX:		
Email:		

SUMMARY OF CHANGES

The following changes have been introduced in Version 2.0 of the protocol

Sections Affected	Changes
Synopsis and Section 4.1 – Inclusion Criteria	Revised: 2. Patients with a PGA score of "minimal" or less and a hsCRP and SAA value within the normal range (≤10 mg/L), and who are considered to have achieved that response as a result of successful anti-IL-1 therapy.
Synopsis and Section 4.2 – Exclusion Criteria	Revised: 4. History of being immunocompromised, including a positive HIV test result at screening. (ELISA and Western blot) test result.
Synopsis, Section 5.2.1.1 – Maintenance of Disease Remission and Clinical Remission, Section 8.4.1 – Efficacy Analyses	Revised and Added: Revised definition of disease remission and added clinical remission.
Synopsis, Table 1 – Schedule of Assessments, and Section 5.4 – Pharmacokinetics and Pharmacokinetics	Added: Pharmacokinetics added as an exploratory endpoint.
Table 1 – Schedule of Assessments and Section 3.1 – Overall Study Design and Plan	Revised: Clarified that the patient diary will be completed beginning 7 days prior to the administration of ATI-450 (Day 1), or immediately beginning at the screening visit if Day 1 is scheduled to occur less than 7 days after baseline. Reduced requirement for patient to complete the patient diary from completion of the study to the completion of the follow up Day 7
Table 1 – Schedule of	visit Added:
Assessments	KSS to be calculated during the screening period.
Table 1 – Schedule of Assessments	Revised: Visit 6 and 7 physical examinations have been changed from full physical exams to brief physical exams.

Table 1 – Schedule of Assessments	Added: Administration of morning dose of ATI-450 in clinic.
Appendix 1 – Possible Hy's Law Liver Chemistry Action and Follow-up Assessments	Revised: Serum acetaminophen to be tested using enzyme immunoassay instead of high liquid chromatography assay.
Appendix 2 – Daily Health Assessment Form	Revised: Daily Health Assessment Form revised because the symptom severity scoring incorrectly ranged from 0 to 9.5 instead of 0 to 10.

PROTOCOL SYNOPSIS

Protocol Number: ATI-450-CAPS-201

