AEs will be coded with the Medical Dictionary for Regulatory Activities (MedDRA). Treatment-emergent adverse events (TEAEs) are defined as AEs with an onset date on or after the date of first administration of study medication and before the date of last administration of study medication + 30 days. TEAEs will be presented by system organ class and preferred term in frequency tables. Patients with multiple AEs will be counted only once within each preferred term and system organ class. Key patient information for patients with an AE with an outcome of death, patients with SAEs, and patients with an AE leading to discontinuation of study medication will be listed.

Laboratory data (hematology, serum chemistry, coagulation, and urinalysis) will be converted to Système International units for reporting and processing purposes. Absolute values and changes from baseline will be presented descriptively. Laboratory data outside study specific reference ranges will be listed. Vital signs and ECG parameters will be presented descriptively.

Handling of Missing Data

Missing data will not be imputed for the safety summaries or the efficacy summaries conducted on the PP population. For efficacy summaries conducted on the ITT population, a model based multiple imputation procedure will be used to impute missing data, where appropriate.

Protocol version and date: 2.0, 24 Sep 2020

SCHEDULE OF ASSESSMENTS

 Table 1
 Schedule of Assessments

Assessment	Screening		12-W	eek Treatment	Period		4-Week Saf	ety Follow-up
	Visit 1 Day -56 to Day -1	Visit 2 Baseline Day 1	Visit 3 Day 14	Visit 4 Day 28	Visit 5 Day 56	Visit 6 Day 84 EOS	Visit 7 Day 7 ⁶	Visit 8 Phone Call Day 30
				(+/-1 day)	•		(+4 days)	(+/-3 days)
Informed Consent	X							
Eligibility Review	X	X						
CAPS and Other Medical	X							
History and Demographics								
QuantiFERON Gold Test for TB	X							
Height	X							
Weight	X							
Physical Exam ¹	X							
Limited Physical Exam		X	X	X	X	X	X	
Physicians Global	X	X	X	X	X	X	X	
Assessment of Disease Activity ²								
Patient Diary (daily) ^{2, 8}	X	X	X	X	X	X	X	
Key Symptom Score ^{2, 8}	X	X	X	X	X	X	X	
HIV and Hep Screen	X	11					11	
SARS-CoV-2 Testing by		X						
RT-PCR								
Vital Signs ^{2, 3}	X	X	X	X	X	X	X	
12-Lead ECG ^{2, 4}	X	X				X		
Hematology, Coagulation,	X	X	X	X	X	X	X	
Chemistry, Lipids, and Urinalysis								

Assessment	Screening		12-W	eek Treatment	Period		4-Week Saf	ety Follow-up

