	Visit 1 Day -56 to Day -1	Visit 2 Baseline Day 1	Visit 3 Day 14	Visit 4 Day 28	Visit 5 Day 56	Visit 6 Day 84 EOS	Visit 7 Day 7 ⁶	Visit 8 Phone Call Day 30
				(+/-1 day)			(+4 days)	(+/-3 days)
PD Blood Sampling ²		X	X	X	X	X	X	
PK Blood Sampling ²		X	X	X	X	X	X	
Serum Pregnancy	X							
Urine Pregnancy		X	X	X	X	X	X	
Dispense Study Medication		X	X	X	X			
Administration of Morning Dose of ATI-450 in Clinic ⁷		X	X	X	X	X		
Drug Accountability			X	X	X	X		
Adverse Events ⁵	X	X	X	X	X	X	X	X
Prior and Concomitant Medications	X	X	X	X	X	X	X	X

ECG=electrocardiogram, Hep=hepatitis, PD=pharmacodynamic, TB=tuberculosis, EOS=end of study

¹A full physical examination will be performed at screening. The brief physical examination (including signs of CAPS) will be performed at visit 6 and follow-up. Body mass index will be derived in the eCRF.

²On dosing day(s), patient diary, PGA, KSS, vitals, clinical laboratory parameters, PK, and PD will be performed before the administration of study medication.

³Vital signs will be measured prior to dosing and immediately following dosing in a semi supine position after 5 minutes' rest and will include temperature, systolic and diastolic blood pressure, pulse, and respiratory rate.

⁴ A triplicate 12-lead ECG will be recorded after the subject has been resting for at least 5 minutes in a supine position.

⁵Serious adverse event reporting will start at the time of consent. Any AE that occurs between the time of consent and dosing on Day 1 will be recorded as medical history. Treatment-emergent AEs will be collected following the first dose of study medication on Day 1.

⁶Patients should not start their anti-IL-1 therapy until all safety follow-up Day 7 assessments have been completed. However, in the event of a safety concern, patients will be allowed to return early or restart their anti-IL-1 therapy early prior to completing the safety follow-up Day 7 visit at the discretion of the investigator.

⁷ The last dose of ATI-450 will be administered in clinic on Day 84. The second dose of ATI-450 is not to be administered on Day 84.

⁸ Patients will be instructed on how to complete their patient diary at the screening visit. Patients will begin completing the patient diary 7 days prior to beginning ATI-450 administration (Day 1), or immediately beginning at the screening visit if the Day 1 visit is scheduled to occur less than 7 days after screening.

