3 STUDY PLAN

3.1 Overall Study Design and Plan

The study visit schedule and planned assessments at each visit are detailed in Table 1.

This is a Phase 2a, open-label, single-arm study to investigate the safety, tolerability, efficacy, PK, and PD of ATI-450 to maintain remission in patients with CAPS previously managed with anti-IL-1 therapy. Up to 10 patients are planned to be enrolled in the study. The study will consist of an up to 8-week screening period, a 12-week treatment period, and a 4-week safety follow-up period. The total duration of the study for patients remaining in the study until their final safety follow-up assessment will be up to 24 weeks.

The investigator will obtain signed informed consent from the patient before any study procedures are performed. For further details regarding the informed consent process, see Section 9.3. During the screening visit each patient will be required to have all assessments performed as outlined in the Schedule of Assessments (Table 1).

Patients whose eligibility is confirmed at baseline will begin dosing ATI-450 tablets (50 mg BID). Such patients will be in protocol-defined remission due to prior treatment with an anti-IL-1 biologic. Dosing will begin on the day that the next dose of their anti-IL-1 therapy is scheduled at which time anti-IL-1 therapy will be discontinued.

The first dose of ATI-450 (50 mg BID) will be taken at the following times (based on anti-IL-1 therapy):

- Anakinra: 24 hours (+/- 1 hour) after last administration or at approximate time of regular anakinra dose.
- Canakinumab: 8 weeks (+/- 1 week) after last administration.
- Rilonacept: 1 week (+/- 1 day) after last administration.

ATI-450 will be administered orally for 12-weeks. Patients will attend clinic visits on Days 14, 28, 56, and 84 (+/-1 day) for safety, efficacy, PK and PD assessments. Patients will begin recording disease symptoms in their daily diary card 7 days prior to beginning administration of ATI-450, or immediately starting at the screening visit if the Day 1 visit is scheduled to occur less than 7 days after the screening visit. Patients will continue to complete their diary until completion of the safety follow up Day 7 visit.

At the end of 12-weeks, Day 84 (+/- 1 day), patients will stop ATI-450 and conduct end of study assessments. Patients will complete safety follow-up visits on site 7 Days (+4 days) after the last dose of ATI-450 and via a phone call 30 Days (+/-3 days) after the last dose.

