5.2.2 Patient Completed Efficacy Questionnaires

When these assessments are required at the times outlined in Table 1, they should be the first tasks done at any visit, and prior to study medication dosing.

The KSS is derived from the patient-administered DHAF (Appendix 2), and is the average on a 0 to 10 scale (0 = None, 10 = Very Severe) of 5 separate scales – rash, feeling of fever and chills, joint pain, eye redness and pain, and fatigue.

The DHAF is designed using a linear rating scale of circles in half-step units (e.g. 0.5, 1.0, 1.5, 2.0, etc.), which are marked 0 (none, no severity) to 10 (very severe)^{2.5}. Patients will select the circle on the scale that they determine most accurately represents severity of the symptom that they have experienced during the last 24 hours.

The DHAF will be completed daily by the patient. Daily KSS will be calculated by averaging the sum of the 5 individual symptom scores. KSS during a specified time period will further be calculated by averaging the sum of daily KSS scores during the time period.

Patients will be provided a quiet, private place to complete the assessments. Patients will be instructed to answer all the questions to the best of their ability and without help from others (study staff, family, or friends). The study staff should review the questionnaires after they are completed and encourage patients to complete any missing information. Patients can refrain from answering any question. Study staff will record the refusal of patients to answer any question in the source documents.

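### Read literally, the only baseline rule makes the KSS baseline one diary day, although the 6-of-8-week endpoint sets a mean KSS against it and up to 7 earlier pre-dose diary days are available

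*Combined protocol and SAP*

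**What the plan says.** Section 8.1 defines baseline once, for all variables: "Baseline is defined as the last non-missing measurement before or on the date of first administration of study medication". No section gives a separate rule for KSS. Section 8.1 leaves further detail to the analysis plan: "The SAP will provide a detailed description of the statistical methods and expand on the details provided in the protocol".

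Section 5.2.2 makes KSS a daily score, the average of five symptom scales from 0 to 10. It adds a period version: "KSS during a specified time period will further be calculated by averaging the sum of daily KSS scores during the time period". No baseline period is specified.

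The diary starts before treatment. Table 1, footnote 8, says: "Patients will begin completing the patient diary 7 days prior to beginning ATI-450 administration (Day 1), or immediately beginning at the screening visit", the second case applying when screening is less than 7 days before Day 1. Section 3.1 says the same. Table 1, footnote 2, places the diary and KSS before dosing on dosing days.

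Three analyses use the KSS baseline:
- **6-of-8-week endpoint** (Table 2, section 8.4.1): a mean KSS no more than 2 points above baseline in at least 6 of 8 weeks.
- **Re-emergence** (section 5.2.2.1): a daily KSS at least 3 above baseline on at least two consecutive days.
- **KSS change from baseline** (section 8.4.1): the text does not say whether a mean is used.

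**The concern.** Applied as written, the rule picks the last single diary score, normally the pre-dose Day 1 form, and leaves the earlier run-in forms unused. In the 6-of-8-week endpoint a weekly mean of several days is then set against one day.

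The weekly means carry their own sampling error, which partly evens out over eight weeks. The baseline error does not, because the same value is subtracted every week. An unusually good baseline day lowers the cut-off for the whole period, and an unusually bad one raises it. With at most 10 patients, one misclassified patient moves the reported proportion by at least 10 percentage points (1/10).

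Two places hint at a run-in score. Footnote 8 is attached to the KSS row of Table 1, and the version 2.0 change log says "KSS to be calculated during the screening period". Neither calls that score the baseline. A programmer could defend either version, and the two classify some patients differently.

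**Working it through.** The plan has no figure to reproduce: section 8.3 sets the sample size by feasibility, and no KSS SD or day-to-day correlation is given.

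**Step 1: the literal baseline.** KSS is one value per diary day (section 5.2.2). The Day 1 form precedes dosing (Table 1, footnote 2). The last non-missing value on or before the first-dose date is therefore the Day 1 score, or the latest earlier form if that is missing. With 7 earlier days and Day 1, up to 8 forms exist; the rule uses one.

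**Step 2: precision of the difference.** Let daily scores have variance σ² and lag-one correlation ρ (an AR(1) pattern, assumed). The variance of an n-day mean, in units of σ², is

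vₙ = [n + 2 Σₖ₌₁ⁿ⁻¹ (n − k) ρᵏ] / n².

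Treating baseline and treatment weeks as uncorrelated, the SD of (weekly mean − baseline) with one day, relative to a 7-day mean, is √[(1 + v₇)/(v₇ + v₇)].

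| ρ | v₇ | SD ratio, one day v 7-day mean |
|---|---|---|
| 0 | 0.143 | √(1.143/0.286) = 2.00 |
| 0.3 | 0.240 | √(1.240/0.480) = 1.61 |
| 0.5 | 0.348 | √(1.348/0.696) = 1.39 |
| 0.7 | 0.518 | √(1.518/1.036) = 1.21 |

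For short run-ins the advantage shrinks. Against a 3-form mean the ratios are 1.55, 1.31, 1.19 and 1.09; against 2 forms they are 1.33, 1.18, 1.11 and 1.05.

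**Step 3: patient classification.** This was simulated with 100,000 patients per setting. Assumptions:
- Daily KSS is gamma distributed with true baseline mean 0.5 or 1.5 and day-to-day SD 0.5 or 1.0, held within 0–10 and rounded to 0.1 (half-point steps averaged over five items).
- Day-to-day correlation is 0, 0.5 or 0.7, through an AR(1) Gaussian copula.
- The true rise is constant over 8 weeks of 7 days that directly follow baseline. The plan does not say which 8 of the 12 treatment weeks count.
- Success is a weekly mean minus baseline of at most 2 in at least 6 weeks. A result is wrong if it disagrees with the true rise.

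Percent misclassified, one-day baseline v 7-day mean:

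| True rise | Baseline, SD | ρ = 0 | ρ = 0.5 | ρ = 0.7 |
|---|---|---|---|---|
| +1, wrong failure | 0.5, 0.5 | 0 v 0 | 0.1 v 0 | 0.6 v 0.3 |
| | 0.5, 1.0 | 2 v 0.3 | 9 v 5 | 14 v 10 |
| | 1.5, 0.5 | 1.3 v 0 | 2.2 v 0.1 | 3 v 0.9 |
| | 1.5, 1.0 | 20 v 1 | 24 v 10 | 25 v 17 |
| +3, wrong success | 0.5, 0.5 | 4 v 0 | 4 v 0.4 | 4 v 1 |
| | 0.5, 1.0 | 9 v 1.4 | 8 v 4 | 8 v 5 |
| | 1.5, 0.5 | 3 v 0 | 2.5 v 0.1 | 2.4 v 0.5 |
| | 1.5, 1.0 | 12 v 0.6 | 11 v 4 | 11 v 6 |

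Repeat runs with other seeds agree within about 1 point, and using 8 forms in place of 7 changes these errors by about 1.1 points or less. With no true change, wrong failure is at most 1.3% v 0.5%. Closer to the cut-off, at a true rise of 2.5, the smallest gain is 12% v 11% (baseline 0.5, SD 1.0, ρ = 0.7). The 7-day mean was equal or better in every setting.

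**The case against.** **The SAP may settle it.** Section 8.1 is a general section that defers detail, section 5.2.2 already defines a period mean, and a run-in diary is collected. An averaged baseline may well be what the sponsor intends, and a rule in the SAP cannot be excluded. That stands as to intent. It does not remove the point: section 8.1 is unqualified and already yields one day for KSS, so a SAP that used a mean would depart from it rather than add detail.

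**Stable patients.** A reader might infer that one good diary day turns a stable patient into a failure. The figures do not support that. KSS cannot fall below 0, so a stable patient with a true mean of 0.5 or 1.5 is on average at most 1.5 points above any baseline day, inside the 2-point limit.

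**Typical size.** A reader might also take 20% v 1% as the usual gain. It needs SD 1.0, true baseline 1.5 and no day-to-day correlation, none of which the documents supply. Patients enter with a PGA of minimal or less, and averaging five items should damp daily variation. At SD 0.5, wrong failure at a rise of 1 is at most about 3% v 1%.

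**A run-in mean is not neutral.** Day 1 is the day the next anti-IL-1 dose is due (section 3.1). For weekly rilonacept, a 7-day run-in covers a whole dosing interval, so its mean may describe something slightly different from the last pre-dose day. The simulation assumes a constant level before treatment and cannot show this. It is a real but small drawback, and a reason to show both versions.

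**Conclusion.** The point holds at modest weight. The plan's only baseline rule, taken literally, gives KSS a one-day baseline while the 6-of-8-week endpoint averages. The mismatch of a mean against one day is clear only for that endpoint; re-emergence compares daily scores, though it and KSS change share the same baseline error.

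Under the stated assumptions a run-in mean lowers misclassification of patients who have truly risen by 1 point (0–25% down to 0–17%) or by 3 points (about 2–12% down to 0–6%). The gain is small when day-to-day SD is low or correlation is high. At correlation 0.7 much of the error remains.

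It would be too strong to call the endpoint invalid. It is exploratory in the synopsis and secondary in Table 2, and it is summarised descriptively without a test in up to 10 patients. No sample-size or error-rate claim depends on it.

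**What to change.** Define baseline KSS as the mean of all available daily KSS from 7 days before Day 1 through the pre-dose Day 1 form (up to 8 forms). The Day 1 form belongs in the mean because it precedes dosing and records what "most accurately represents severity of the symptom that they have experienced during the last 24 hours" of the patient's experience.

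- Use this baseline for the 6-of-8-week endpoint, re-emergence and KSS change.
- Report the number of forms contributing for each patient, and flag those below a pre-set number, for example 3.
- Show the last-day baseline as a sensitivity summary, because the run-in may span an anti-IL-1 dosing interval.
- State in the same place which 8 of the 12 weeks count.

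Put the rule in the SAP before the data are reviewed, and align section 8.1 with it. If the SAP already holds a KSS rule, only the alignment is needed. The cost is wording and one extra summary, with no new data, visits or patients. Changing section 8.1 itself follows the amendment process in section 12.
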